4.1 Primary Endpoints and Assessment Methods

See Table 3.1 of the protocol for endpoints. For Assessments methods, see protocol Section 8.2.1.1 for primary immunogenicity; and see protocol Section 8.4 for primary safety.

4.2 Secondary Endpoints and Assessment Methods

See Table 3.1 of the protocol for endpoints. For Assessments methods, see protocol Section 8.2.1.1 and Section 8.2.1.2 for secondary immunogenicity; And see protocol Section 8.2.2 for secondary efficacy;

4.3 Exploratory Endpoints and Assessment Methods

See Table 3.1 of the protocol for endpoints. For Assessments methods, see protocol Section 8.2.1.2 for exploratory immunogenicity and 8.2.1.3 for cellular-mediated immunity.

4.4 Derived Endpoints: Calculation Methods

4.4.1 Safety

The safety analysis will include all events or reactions with time of onset before the date of receiving a non-study authorized/approved COVID-19 vaccine and will include only the corresponding safety data collected before the date of receiving a non-study authorized/approved COVID-19 vaccine. The endpoints derivations for safety analysis are detailed in the following sections. Events or reactions with time of onset on or after the date of receiving a non-study authorized/approved COVID-19 vaccine will be listed separately.

4.4.1.1 Solicited Reactions

4.4.1.1.1 Daily Intensity

All daily records for solicited reactions will be derived into daily intensity according to the following classification: None, Grade 1, Grade 2, Grade 3, or Missing.

For measurable injection site reactions:

- None: > 0 to < 25 mm
- Grade 1: ≥ 25 to ≤ 50 mm
- Grade 2: ≥ 51 to ≤ 100 mm
- Grade 3: > 100 mm

For Fever:

- None: $< 38.0^{\circ}\text{C}$ or $< 100.4^{\circ}\text{F}$
- Grade 1: $\geq 38.0^{\circ}\text{C}$ to $\leq 38.4^{\circ}\text{C}$ or $\geq 100.4^{\circ}\text{F}$ to $\leq 101.1^{\circ}\text{F}$
- Grade 2: $\geq 38.5^{\circ}\text{C}$ to $\leq 38.9^{\circ}\text{C}$ or $\geq 101.2^{\circ}\text{F}$ to $\leq 102.0^{\circ}\text{F}$
- Grade 3: $\geq 39.0^{\circ}\text{C}$ or $\geq 102.1^{\circ}\text{F}$

For the derivation of daily intensities, the following sequential steps will be applied:

- 1) Solicited reactions (except fever/pyrexia) with an Investigator presence recorded as “No” and with all daily records missing then all daily intensities will be derived as None.
- 2) For non-measurable solicited reactions, daily intensities will correspond to daily records reported in the clinical database. For measurable solicited reactions the daily measurements reported in the clinical database will be converted based upon the intensity scales defined in the protocol; this assumes a reaction that is too large to measure (non-measurable, “NM”) is Grade 3. Note the intensity could be considered “None” (not a reaction) in the analysis despite being considered a reaction by the investigator (e.g., swelling measurement > 0 mm but < 25 mm in adults).

Note: The maximum intensity on the ongoing period is derived from the record of the maximum intensity/measurement after the end of the solicited period following the rule described above.

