4.4.1.1.2 Maximum Intensity

Maximum intensity is derived from the daily intensities computed as described in Section 4.4.1.1.1 and is calculated as the maximum of the daily intensities over the period considered.

Note: The maximum intensity could be considered “None” (not a reaction) in the analysis despite being considered a reaction by the investigator (e.g., swelling measurement > 0 mm but < 25 mm in adults).

For those participants receiving a non-study authorized/approved COVID-19 vaccine (e.g., on Day X) within the solicited collection period, the maximum intensity of solicited reactions in safety analysis is derived on daily intensities from D01 to Day X-1.

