4.4.1.1.3 Presence

Presence is derived from the maximum overall intensity on the period considered:

- None: No presence
- Grade 1, Grade 2, or Grade 3: Presence
- Missing: Missing presence

Subjects with at least one non-missing presence for a specific endpoint will be included in the analysis. Conversely, those without a non-missing presence will not be included in the analysis of the endpoint.

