4.4.1.4.6 AEs Leading to Study Discontinuation

A flag will be available in the clinical database for all AEs in order to identify AEs leading to discontinuation.

In general, the items that are counted are:

- For subject disposition: if subject did not complete the study due to AE as recorded in Completion at End of Study form
- For safety overview: if subject did not complete the study due to AE as recorded in Completion at End of Study form or had any solicited or unsolicited AEs causing study discontinuation / termination as recorded in solicited reaction or unsolicited AE forms within the time period indicated
- For summary of unsolicited AEs by system organ class (SOC) / PT: A solicited AE that has “Caused Study Termination” checked that is at least Grade 1 or an unsolicited AE that has “Caused Study Termination” checked that is at least Grade 1 or missing and is within the time period indicated

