5.3.1.4 Intensity

For solicited reactions, missing intensities will be handled as described in [Section 4.4.1.1.1](#). For unsolicited non-serious AEs, missing intensities will remain missing and will not be imputed.

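### For solicited reactions other than fever, when every daily record is missing the SAP keeps an Investigator 'No' as a non-reactor but leaves an Investigator 'Yes' out, which biases the reported rate downward

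*SAP*

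**What the plan says.** SAP 4.4.1.1.1 derives daily intensity in two steps. Step 1 uses the Investigator's overall presence flag in one direction. It covers "Solicited reactions (except fever/pyrexia) with an Investigator presence recorded as" negative, so fever is exempt. The consequence when the diary is blank is spelled out: "and with all daily records missing then all daily intensities will be derived as None". Step 2 uses only what was recorded day by day: "For non-measurable solicited reactions, daily intensities will correspond to daily records reported in the clinical database", and measured sizes are converted to grades.

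SAP 4.4.1.1.2 says that maximum intensity "is calculated as the maximum of the daily intensities over the period considered". SAP 4.4.1.1.3 derives presence from the maximum, with the mapping "Missing: Missing presence", and adds that "those without a non-missing presence will not be included in the analysis of the endpoint".

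The missing-data section gives no further rule. SAP 5.3.1 says that replacement is generally not done, and 5.3.1.4 points back: "For solicited reactions, missing intensities will be handled as described in" 4.4.1.1.1.

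A related difference appears in SAP 4.4.1.4.6. In the summary by system organ class and preferred term, an unsolicited AE that led to termination counts if it has that box "checked that is at least Grade 1 or missing and is within the time period indicated". A solicited one counts only if it is at least Grade 1.

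**The concern.** Accepting an Investigator 'No' when the diary is blank is reasonable on its own. The difficulty is that 'Yes' has no counterpart. Of two participants with the same blank diary, the one reported as having no reaction is kept and the one reported as having a reaction is left out. Membership of the analysis then depends on the outcome being estimated.

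Presence of solicited reactions after each injection is a primary safety endpoint (Protocol Table 3.1), and the stated aim is to describe safety in all participants. Arms have 10 to 60 participants per age stratum (Protocol Table 4.2), so a single lost reactor is visible.

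The rule also runs against the SAP's usual direction. Missing causality is taken as related (5.3.1.2), a missing Immediate field as within 30 minutes (5.3.1.1), and an AE with missing onset stays in the 21-day tables (4.4.1.2.4). A reaction too large to measure is Grade 3 (4.4.1.1.1).

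**Working it through.** **Scope.** Protocol Tables 10.2 and 10.3 list seven solicited reactions: pain, erythema, swelling, fever, headache, malaise and myalgia. Step 1 exempts fever, so six are affected. For fever, 'Yes' and 'No' with all temperatures missing are both left out.

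**Tracing the rule when all daily records are missing (non-fever).**

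| Investigator flag | Daily intensity | Maximum | Presence | In the analysis? |
|---|---|---|---|---|
| No | None (step 1) | None | No | Yes, as a non-reactor |
| Yes | Missing (step 2) | Missing | Missing | No |

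The second row is an inference from three subsections; the SAP does not write it out.

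**Formula.** The plan states no expected reaction rate and no missing-diary rate, so there is no figure to reproduce. Let p be the true rate and m the share of participants with no daily record at all, and assume that the flag is correct. All non-reactors are kept, so only the missing share among reactors matters.

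- Numerator share: p(1 − m). Denominator share: 1 − pm.
- Reported rate: p(1 − m)/(1 − pm).
- Bias: −pm(1 − p)/(1 − pm), which is negative whenever 0 < p < 1 and m > 0.

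Example, p = 50% and m = 5%: 0.475/0.975 = 48.7%, a bias of −1.3 points.

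| Assumed m | p = 10% | p = 50% | p = 90% |
|---|---|---|---|
| 2% | −0.2 | −0.5 | −0.2 |
| 5% | −0.5 | −1.3 | −0.5 |
| 10% | −0.9 | −2.6 | −1.0 |

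(Percentage points.) The bias peaks near p = 50% and falls away on both sides.

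**Arm-level examples (Clopper-Pearson 95% intervals; the splits are assumed).**

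- n = 60 with 30 reactors; 3 'Yes' and 3 'No' with blank diaries. Flag used both ways: 30/60 = 50.0% (36.8 to 63.2). SAP rule: 27/57 = 47.4% (34.0 to 61.0). Both dropped: 27/54 = 50.0% (36.1 to 63.9).
- n = 20 with 10 reactors; one of each blank. 10/20 = 50.0% (27.2 to 72.8) becomes 9/19 = 47.4% (24.4 to 71.1).
- n = 20 with 4 reactors, one ungraded: 4/20 = 20% becomes 3/19 = 15.8%.

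In the first example either symmetric treatment recovers 50%; the one-sided rule does not. Pooling arms narrows the interval but does not remove the bias.

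**Between-group differences at m = 10%.** At 70% versus 15%, the reported rates are 67.7% and 13.7%, and the difference goes from 55.0 to 54.0 points. At 90% versus 30%, they are 89.0% and 27.8%, and it goes from 60.0 to 61.2 points.

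**Erythema and swelling.** A size below 25 mm is analysed as None even if the Investigator recorded a reaction. Suppose 40% have a reaction of some size, half of these reach 25 mm, and m = 10%. The true rate is 20%. The SAP rule gives 0.20 × 0.90/(1 − 0.40 × 0.10) = 0.18/0.96 = 18.75%. Counting every unmeasured 'Yes' as present gives 0.18 + 0.04 = 22%. The SAP rule is too low, and automatic presence is too high.

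**The case against.** The strongest reply is that the case should be rare. One recorded day is enough to keep a participant in. Protocol 8.4.2 has the site interview participants, clarify incomplete diary entries and report what the diary lacks, so an Investigator who establishes 'Yes' will usually obtain a grade or size. The study is descriptive, and the bias at low missingness is small beside the intervals. All of this stands and limits the size. It does not remove the asymmetry: the interview that makes a 'No' credible makes a 'Yes' equally credible.

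Second, presence is derived from the maximum overall intensity on the period considered, and 4.4.1.1.1 also derives a maximum for the ongoing period. If that counts, a 'Yes' with a recorded later maximum could be retained. The SAP should say which reading applies.

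A reader might infer several stronger things that the documents do not support:

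- *All solicited rates are biased.* Fever is exempt from step 1.
- *Active-versus-placebo differences always shrink.* They can widen, as the 90% versus 30% case shows.
- *The bias is large.* Missingness of 15 to 20% has no basis in the documents.
- *Every dropped 'Yes' is a lost reactor.* For erythema and swelling it may be below 25 mm.
- *An ungraded solicited reaction that ended participation disappears from the report.* It is absent only from the summary by system organ class and preferred term. The safety-overview item in 4.4.1.4.6 counts it with no grade condition, and the disposition item counts non-completion due to an AE.
- *The early safety review is affected.* Its criteria in Protocol 8.4 are participant counts, not these percentages.

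**Conclusion.** The concern holds for the six non-fever reactions. As written, the SAP keeps an ungraded 'No' and, by inference, leaves out an ungraded 'Yes', so the expected rate for a primary safety endpoint is biased downward whenever such a 'Yes' occurs. If none occurs, the bias is zero.

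The size is modest: at an assumed 2 to 5% of participants without any daily record, at most about 1.3 percentage points, inside the arm-level intervals. This rests on a correct Investigator flag and on no rescue through the ongoing-period maximum. For erythema and swelling the expected direction is also downward, but an individual case is of unknown status. No direction can be claimed for between-group differences. The point deserves correction because the error is systematic and cheap to remove, not because it is likely to change the safety picture.

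**What to change.** 1. In SAP 4.4.1.1.1 and 4.4.1.1.3, for pain, headache, malaise and myalgia: when Investigator presence is 'Yes' and no daily grade exists, set presence to Yes and maximum intensity to Missing. Keep the participant in numerator and denominator, and show a 'Grade missing' row with counts by arm.
2. For erythema and swelling, do the same as a sensitivity analysis and report how many cases rest on an unmeasured reaction.
3. State whether a maximum recorded in the ongoing period enters the presence derivation.
4. In the system organ class and preferred term summary of 4.4.1.4.6, let a solicited AE that caused termination count when its grade is missing, as an unsolicited one does. This brings the table into line with the safety overview.
5. Record the change as made after the partial database lock noted in SAP 5.4 and Protocol 9.5.

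The cost is a few SAP sentences, one table row and one small sensitivity table. Reported rates may rise slightly, and in the sensitivity analysis some reactions below 25 mm may be counted.

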4.4.1.1.2 Maximum Intensity

Maximum intensity is derived from the daily intensities computed as described in Section 4.4.1.1.1 and is calculated as the maximum of the daily intensities over the period considered.

Note: The maximum intensity could be considered “None” (not a reaction) in the analysis despite being considered a reaction by the investigator (e.g., swelling measurement > 0 mm but < 25 mm in adults).

For those participants receiving a non-study authorized/approved COVID-19 vaccine (e.g., on Day X) within the solicited collection period, the maximum intensity of solicited reactions in safety analysis is derived on daily intensities from D01 to Day X-1.

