and rapid communication by the Investigator to the Sponsor can be appropriate. Such an event might warrant further investigation in order to characterize and understand it. Depending on the nature of the event, rapid communication by the study Sponsor to other parties (eg, regulators) might also be warranted.

New-Onset Chronic Medical Conditions (NOCMCs): NOCMCs are defined as any new ICD-10 diagnosis (10th revision of the International Statistical Classification of Diseases and Related Health Problems) that is applied to the participant during the course of the study, after receipt of the study agent, that is expected to continue for at least 3 months and requires continued health care intervention.

Potential Immune-Mediated Disease (pIMDs): pIMDs constitute a group of AEs that includes diseases which are clearly autoimmune in etiology and other inflammatory and/or neurologic disorders which may or may not have autoimmune etiologies. pIMDs currently in effect are presented in [Appendix 10.5:Adverse Events of Special Interest](#).

Reactogenicity / Solicited Reactions

A solicited reaction is an “expected” adverse reaction (sign or symptom) observed and reported under the conditions (nature and onset) pre-listed in the protocol and CRF (eg, injection site pain or headache occurring between the day of vaccination and the next 7 days).

By definition, solicited reactions are considered as being related to the study intervention administered.

For injectable vaccines, solicited reactions can either be solicited injection/administration site reactions or solicited systemic reactions.

Unsolicited AE/AR

An unsolicited AE is an observed AE that does not fulfill the conditions of solicited reactions, ie, pre-listed in the CRF in terms of diagnosis and/or onset window post-vaccination. For example, varicella or a solicited term such as headache starting after the solicited observation period (headache starting on Day 10 post-vaccination in the case where headache occurring between the day of vaccination and the next 7 days is pre-listed in the protocol and CRF as a solicited reaction).

An unsolicited AR is an unsolicited AE that is considered related to study intervention. Unsolicited AEs includes both serious (SAEs) and non-serious unsolicited AEs.

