4.4.1.1.6 Overall Number of Days of Occurrence

If a reaction is ongoing at the end of the solicited period, then the overall number of days of occurrence is derived from the daily intensities and the stop date of the reaction after the end of the solicited period. The overall number of days of occurrence is:

- (stop date – last vaccination date) + (number of days of occurrence within the solicited period) – length of the solicited period + 1

If the stop date is missing or incomplete (contains missing data [MD]), the overall number of days of occurrence will be considered as Missing. If a participant received a non-study authorized/approved COVID-19 vaccine within the solicited period and the solicited reaction is ongoing at the time of the receipt of the authorized/approved COVID-19 vaccine, the overall number of days of occurrence will be analyzed as Missing for main safety analysis.

Table 4.3: Categories for overall number of days of occurrence

Injection Site Reactions (D01-D08)	Systemic Reactions (D01-D08)
1-3 days	1-3 days
4-7 days	4-7 days
8 days or more	8 days or more
Missing	Missing

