4.4.1.1.7 Ongoing

Ongoing is derived from the last daily intensity of the solicited period computed as described in [Section 4.4.1.1.1](#) and the maximum intensity in the ongoing period. The Investigator's ongoing flag is not used because the measurement would determine the ongoing status of the reaction.

- Ongoing: if the last daily intensity of the solicited period is at least Grade 1 and the maximum intensity on the ongoing period is at least Grade 1
- Not ongoing: if the last daily intensity of the solicited period is None or the maximum intensity on the ongoing period is None.
- Missing: all other conditions (in this case, it is not included in the denominator of the ongoing analysis in the safety tables).

If a participant received a non-study authorized/approved COVID-19 vaccine within the solicited period, the ongoing status will be derived as “Missing”.

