5.1.1.2 Statistical Methods for Primary Safety Objective

Safety results will be described for each age and vaccine group. The homogeneity of pooled groups will be assessed on the main parameters. The main parameters will be described with 95% CI.

Safety analyses will be performed based on safety analysis set including safety data collected before the date of receiving an authorized/approved COVID-19 vaccine. Safety data collected on or after the day of receiving an authorized/approved COVID-19 vaccine will be listed separately.

Solicited Reactions

Number and percentage of subjects with:

- Presence of solicited injection site reactions and systemic reactions occurring up to 7 days after injection
- Each solicited reaction according to time of onset, maximum intensity, and number of days of occurrence over the solicited period

Unsolicited Events and Reactions

Number and percentage of subjects with:

- Any unsolicited immediate systemic event in the 30 minutes after injection
- Any unsolicited event and reaction (using the current MedDRA version) 21 days after injection
- Any unsolicited event/reaction according to time of onset, maximum intensity, and duration

SAEs

Number and percentage of subjects with:

- any SAE within 21 days after injection and during the 6 months and 12 months follow-up periods according to SOC and PT, seriousness and outcome

AEs of special interest

- Number and percentage of subjects with any/each AESI within 21 days after injection and during the 6 month and 12 months follow-up periods will be presented according to SOC and PT, seriousness and outcome.

MAAE

- Presence of medically attended adverse events (MAAEs) throughout the study

Laboratory tests

- Presence of out-of-range biological test results up to 7 days post-last dose (ie, up to D09 for Cohort 1 and up to D30 for Cohort 2)

The following analyses will be performed for laboratory tests in addition to the summary of out of range tests above:

- Biological test results and toxicity grade by visit,

- Summary of toxicity grade shift from baseline,

For descriptive purposes, the statistics presented on [Table 5.1](#) will be produced.

In addition to analyses by each intervention group, aggregated groups will be used to perform complementary assessments for above parameters, including:

1. aggregated vaccine group, ie, all vaccine arms pooled
2. aggregated placebo group, ie, two placebo arms pooled

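### With D08 blank, SAP 4.4.1.1.7 keeps reactions that stopped but drops those that continued, and the post-D08 peak grade has no stated place in the intensity tables

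*SAP*

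**What the plan says.** Solicited reactions are graded daily from D01 to D08 after each injection. For a reaction that continues, the SAP relies on two later items: a stop date and a peak grade. On the peak, SAP 4.4.1.1.1 states: "The maximum intensity on the ongoing period is derived from the record of the maximum intensity/measurement after the end of the solicited period".

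These items are used as follows.

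- **Maximum intensity (4.4.1.1.2)** is derived from the daily intensities and is "calculated as the maximum of the daily intensities over the period considered". The period is not named. SAP 5.1.1.2 lists the tabulation as "Each solicited reaction according to time of onset, maximum intensity, and number of days of occurrence over the solicited period".
- **Presence (4.4.1.1.3)**: "Presence is derived from the maximum overall intensity on the period considered". The SAP does not define an overall intensity.
- **Ongoing status (4.4.1.1.7)** needs a D08 grade of at least Grade 1 and also that "the maximum intensity on the ongoing period is at least Grade 1". A reaction is Not ongoing if either value is None. The remainder is "Missing: all other conditions (in this case, it is not included in the denominator of the ongoing analysis in the safety tables".
- **Overall days (4.4.1.1.6)**: "If a reaction is ongoing at the end of the solicited period, then the overall number of days of occurrence is derived" from the daily grades and the stop date. A missing or incomplete stop date makes the result Missing. The section does not say what happens when ongoing status itself is Missing.

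SAP 5.3.1.4 sends missing solicited intensities back to 4.4.1.1.1. The only fill rule there applies when every daily record is missing and the investigator recorded no reaction. It does not cover one blank day.

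**The concern.** Solicited reactions are a primary safety endpoint, described by age and vaccine group. Severe and prolonged reactions are where adjuvants and doses are most likely to differ.

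The ongoing rule makes inclusion in the denominator depend on the outcome. Among reactions with a blank D08, the ones known to have stopped are counted and the ones known to have continued are not.

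For grade, a peak after D08 is collected and graded, but its only stated use is in setting the ongoing status. Nor would it surface as an unsolicited event. Protocol 10.3.1 says: "An unsolicited AE is an observed AE that does not fulfill the conditions of solicited reactions", and a reaction with onset in the solicited window does fulfil them. The result is uneven. By the protocol's own example, a headache starting on Day 10 is unsolicited, and SAP 4.4.1.2.2 reports it at its highest grade. A headache starting on Day 7 that reaches Grade 3 on Day 10 is reported at its Day 7-8 grade.

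**Working it through.** **Ongoing status.** Applying 4.4.1.1.7 to every combination gives:

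| D08 grade | Ongoing-period maximum | Status | In denominator |
|---|---|---|---|
| Grade 1+ | Grade 1+ | Ongoing | yes |
| None | any value | Not ongoing | yes |
| Grade 1+ | None | Not ongoing | yes |
| blank | None | Not ongoing | yes |
| blank | Grade 1+ | Missing | no |
| Grade 1+ or blank | missing | Missing | no |

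Rows four and five show the asymmetry: the D08 entry is blank in both, and the later record decides whether the reaction counts.

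**Direction.** Let *a* be the reactions classed Ongoing, *n* all reactions in the SAP denominator, and *c* those with D08 blank and a graded ongoing period. The SAP reports *a/n*. Counting the *c* reactions as ongoing gives *(a+c)/(n+c)*. The difference is *c(n−a)/[n(n+c)]*, which is never negative. If only a share *p* of the *c* reactions was truly present on D08, the SAP figure is still too low whenever *p > a/n*.

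**Overall days.** The formula in 4.4.1.1.6 is (stop date − last vaccination date) + graded days in the solicited period − 8 + 1. It is sound when D08 is graded: vaccination D01, graded D01-D08, stop D12 gives 11 + 8 − 8 + 1 = 12 days.

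Now take Grade 1 on D02-D07, D08 blank, a graded ongoing period and stop D14.

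- Status is Missing, so the formula is not triggered.
- The solicited-period count (4.4.1.1.5) is 6 days, category 4-7 days.
- The formula applied unchanged gives 13 + 6 − 8 + 1 = 12 days, one short because D08 is not counted.
- With D08 counted it gives 13 + 7 − 8 + 1 = 13 days, which matches D02 through D14 and falls in the category of 8 days or more.

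A later-onset case: Grade 1 on D06-D07, D08 blank, stop D20. The solicited-period count is 2 days (1-3 days). With D08 counted, the formula gives 19 + 3 − 8 + 1 = 15 days.

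**Grade.** Take Grade 2 on D01-D08, a later peak of Grade 3 and stop D12. The maximum of the daily grades is Grade 2; including the ongoing-period maximum it is Grade 3. Overall duration is 12 days either way.

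**Size per participant** (arm sizes from Protocol Table 4.2): 1/10 = 10 points, 1/20 = 5 points, and 1/90 = 1.1 points in a two-injection AS03 arm with both age groups combined (60 + 30).

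**The case against.** A reader might infer that nothing recorded after D08 is used, or that long reactions are understated in general. The SAP does not support either. The stop date drives overall days and the post-D08 maximum drives ongoing status. A reaction with D08 graded, a graded ongoing period and a complete stop date gets its full duration. Nor does a blank D08 remove a reaction from all duration summaries: the solicited-period count survives, one day short. Overall days is left undefined rather than shown to be shorter. Table 4.3 has a Missing category, and the SAP does not say whether that or the solicited-period count would apply.

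On grade, the primary endpoint covers reactions up to 7 days after each injection, and a D01-D08 maximum fits that window. No text requires a later peak to be reported. The wording is also open: the period in 4.4.1.1.2 is unnamed, and in 5.1.1.2 the solicited period may qualify only the number of days. Table shells are not in the documents, so absence from every table is a reading of silence.

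Blanks should also be uncommon. Diary card 1 is reviewed at D09, at a visit in Cohort 1 and by telephone in Cohort 2. Participants are interviewed at card collection to resolve incomplete entries (Protocol 8.4.2 and the schedules of activities).

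All of this limits the point. It does not repair the blank-D08 rule, because no other section fills a single blank day. It makes the grade issue a reporting gap, not a contradiction of the endpoint.

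**Conclusion.** Two limited points stand.

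**(a) SAP 4.4.1.1.7 is wrong as written.** For a blank D08 it excludes continuing reactions and keeps those that stopped, so the proportion ongoing is biased down, and overall days is undefined for the excluded reactions. The direction assumes that a graded ongoing-period record usually means the reaction was present on D08, which is how the SAP itself uses that record.

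**(b) SAP 4.4.1.1.2 can be improved cheaply.** The D01-D08 maximum is legitimate, but the recorded later peak has no stated place in the intensity tables. For a reaction that peaks later, the displayed grade can only be too low.

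The overall size cannot be computed, because the documents give no frequency of late peaks or blank D08 entries. The per-participant shifts of 10, 5 and about 1 percentage points show what a single case would do to a percentage in a given arm; they do not predict how many cases will occur. The analyses are descriptive (Protocol 9.1), so no test is affected. This is a minor point.

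**What to change.** - **4.4.1.1.7:** classify a reaction as ongoing when the ongoing-period maximum is at least Grade 1 and the D08 grade is at least Grade 1 or missing. Leave the other combinations as they are.
- **4.4.1.1.6:** apply the overall-days formula to these reactions and count the blank D08 as a day of occurrence.
- **4.4.1.1.2:** name D01-D08 as the period for the existing maximum and keep that column. Beside it, tabulate an overall maximum, the higher of the daily grades and the ongoing-period maximum, for reactions with onset in D01-D08. State which of the two maxima 4.4.1.1.3 uses for presence.
- Keep the existing cut at a non-study COVID-19 vaccine for all of these.

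The cost is a few sentences in the SAP and one table column. The SAP already relies on the ongoing-period maximum and the stop date, so no new data are needed. The downside is that a few more Grade 3 or prolonged reactions may be reported.
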